#### *1.3.2.3 Physical Examination*

Physical examinations, including body weight will be conducted at Screening, Day 1, Day 15 of Cycle 1 and Cycle 2 and EOCT.

#### *1.3.2.4 Vital Signs*

Supine and standing systolic and diastolic blood pressure, heart rate, body temperature, respiratory rate will be measured at Screening, Day 1, Day 2, Day 3, Day 15, Day 22, Day 29, Day 36 of each cycle and EOCT.

For the day of infusion vital signs will be measured prior to infusion and at infusion completion (0 minutes), 30±5 minutes, 60±10 minutes, 4 hours ±10 minutes after the end of infusion.

#### *1.3.2.5 Electrocardiography*

An ECG analysis will be included as a safety evaluation/endpoint in this study. Twelve lead-ECG will be recorded at Screening, Day 1 of each cycle and EOCT and 6-hour Holter ECG

will be recorded at Day 1 of each cycle. Twelve lead ECGs will be recorded so that the different ECG intervals (RR, PR, QRS, QT, QTcF) will be measured.

### 1.3.2.6 *Clinical Laboratory Tests*

#### *Haematology*

Blood samples will be collected to assess the following parameters: RBC count, haemoglobin, haematocrit, mean corpuscular volume (MCV), mean corpuscular haemoglobin (MCH), mean corpuscular haemoglobin concentration (MCHC), WBC count with differential (neutrophils, lymphocytes, monocytes, eosinophils and basophils) and platelet count.

#### *Blood Biochemistry*

Blood samples will be collected to assess the following parameters:

- urea, uric acid, creatinine, creatinine clearance, total bilirubin, conjugated bilirubin
- chloride, bicarbonate, sodium, potassium, calcium, phosphate
- alkaline phosphatase, aspartate aminotransferase, alanine aminotransferase, gamma glutamyl transferase
- albumin and total protein, total cholesterol, triglycerides, fasting glucose
- C-reactive protein (CRP)

Estimated glomerular filtration rate (eGFR) will be calculated based on serum creatinine levels using MDRD formula.

#### *Urinalysis*

Urine samples will be collected to assess the following parameters: pH, protein, ketones, bilirubin, blood, urobilinogen, nitrites, leukocytes, glucose. Proteinuria will be performed with dipsticks, in case of positivity, a proteinuria over 24 hours will be performed.

#### *Pregnancy Test*

A  $\beta$  human chorionic gonadotrophin (HCG) serum test will be performed for all female subjects of childbearing potential at Screening (visit 1) and if clinically indicated thereafter. Moreover, a HCG urine test will be performed at Day 1 of each cycle before each 177Lu-OPS201 administration.

#### *Hypothalamic-Pituitary-Adrenal Axis Biomarkers*

Sample for hormone analysis will be collected at predose Day 1 of each Cycle and at EOCT/EOAC visit. These samples include analysis of cortisol, TSH, parathyroid hormone (PTH), luteinising hormone (LH), follicle-stimulating hormone (FSH), free thyroxine (FT4) and IGF-1.

Hormone analyses will only be analysed in subjects who do not have substitution or therapy impacting one of the respective pituitary axis (e.g. no cortisol sampling in subjects who receive corticosteroids, no thyroid-stimulating hormone and free thyroxine sampling in subjects who have thyroxine substitution).

TSH, cortisol and IGF-1 will be measured at baseline and at end of core trial.

#### *Specific Renal Safety Biomarkers*

Renal safety biomarkers include markers specific of the different renal tubule regions toxicity: alpha-glutathione S-transferase (GST), glutathione S-transferase P1 (GSTP1), kidney injury molecule-1 (KIM-1), clusterin, cystatin-C, calbindin, beta-2 microglobulin and creatinine.

Urine samples will be collected at the following timepoints:

- Cycle 1:

SAP Final: Version 2.0: [03 January 2020]

23/57

- Day 1: early morning, before the infusion (baseline)
- Day 3: early morning (48 hours after the end of  $^{177}\text{Lu}$ -OPS201 infusion at the latest)
- End of core trial Visit/Early Withdrawal Visit: early morning.

#### *Specific Pancreatic Function Biomarker*

Samples for specific pancreatic function biomarker will include glycosylated haemoglobin HbA1c and glucose. Blood will be collected at Day 1 of each visit before infusion and End of core trial visit / Early Withdrawal.

#### *Testicular Function Biomarkers*

Samples for Testicular Function Biomarkers will include testosterone, Inhibin B and sex hormone-binding globulin SHBG. Blood will be collected at Day 1 of each visit before infusion and End of core trial visit / Early Withdrawal.

#### *1.3.2.7 Nuclear Medicine Imaging for Dosimetry*

All images will be centralised and analysed by independent readers for dosimetry analysis of the dose limiting organs and tumour lesions.

To determine the biokinetics and perform an absolute quantification, whole body scans (planar scintigraphy) and SPECT/CT will be performed at each cycle at the following timepoint ranges just after the end of  $^{177}\text{Lu}$ -OPS201 infusion:

- Day 1: 2 to 4 hours
- Day 2: 16 to 24 hours
- Day 3: 40 to 48 hours
- Day 4 to Day 5: 72 to 96 hours
- Day 6 to Day 7: 144 to 168 hours.

At the timepoint between 16 to 24 hours, SPECT/diagnostic CT will be performed. For all other time points, SPECT/low dose CT will be performed.

For subjects receiving additional administrations (up to four additional cycles), dosimetry assessments will be performed after each additional administration with nuclear medicine imaging described above.

#### *1.3.2.8 Pharmacokinetics of OPS201*

##### *Blood Sample Collection*

For each subject, OPS201 plasma concentration will be measured. Each subject will have blood samples collected at Cycle 1 only at the following time points:

- Day 1: before the infusion (baseline), at the end of infusion of  $^{177}\text{Lu}$ -OPS201 (0),  $5\pm 1$  minutes,  $30\pm 5$  minutes, 1 hour ( $\pm 5$  minutes) and 4 hours ( $\pm 30$  minutes), 6 ( $\pm 30$  minutes), and  $10\pm 1$  hours after the end of infusion.
- Day 2:  $24\pm 2$  hours after the end of infusion of  $^{177}\text{Lu}$ -OPS201.
- Day 3:  $48\pm 2$  hours after the end of infusion of  $^{177}\text{Lu}$ -OPS201.

##### *Urine Sample Collection*

The samples for urine OPS201 concentration analysis will be taken from urine collected during four different periods at Cycle 1: from 0 to 4, 4 to 8, 8 to 24 and 24 to 48 hours (0 to 4 and 4 to 8 hours only in US sites) after the start of infusion, with an initial void collection shortly before the infusion (0) and a final collection, 48 hours after the end of  $^{177}\text{Lu}$ -OPS201 infusion.

SAP Final: Version 2.0: [03 January 2020]

24/57

### *1.3.2.9 Exploratory Biomarkers and Biobanking*

#### *DNA-DSB in Peripheral Lymphocytes*

DNA-DSB in lymphocytes will be measured using an immunofluorescent method in selected sites. DNA-DSB will be measured in lymphocytes (n=6 per cycle) before the infusion (baseline), at 1, 4, 24, 48 and 72 to 96 hours after the end of Lu-OPS201 infusion (Cycle 1 and Cycle 2).

#### *DNA Repair Capacity in Peripheral Lymphocytes*

DNA repair capacity in lymphocytes will be measured using an enzymatic method in selected sites.

#### *Germinal Mutation in Blood*

Blood sample will be collected in a Paxgen-DNA tube at Cycle 1 Day 1 before infusion from the arm opposite to that of the study drug infusion or from another site.

#### *Tumour Biopsy*

Sequential biopsies will be obtained at Screening and EOCT or at disease progression, whichever occurs earlier. Baseline biopsy is mandatory and post-treatment biopsy is optional.

#### *Tumour Micro-environment and Other Markers of Interest*

The biopsy will be used to evaluate tumour microenvironment and other markers of interest of the disease, such as: proliferative marker (ki-67), Tumour infiltrating immune cells (TIL/TME), DNA-DSB (gammaH2AX), target receptor evaluation (sstr2), tumour gene expression profile and gene mutations (targeted or TMB).

Specific markers depending on the indication will also be assessed in tumour biopsy (i.e. for BC: ER, progesterone receptor and HER2 protein expression and for SCLC: p53, Rb1, MYC and DLL3 gene expression).

#### *DNA Repair Capacity in Tumour Tissue*

DNA repair capacity will be measured in tumour tissue by a specialised laboratory in case sufficient material is available (biopsy larger than 5 mm^3).

#### *Biobanking*

Analysis of biobank samples will be performed outside the scope of the main study and will be reported separately. Therefore, this analysis is optional.

### *1.3.2.10 Withdrawal/discontinuation*

In accordance with the Declaration of Helsinki (in accordance with the applicable country's acceptance), each subject is free to withdraw from the study at any time. The investigator also has the right to withdraw a subject from the study in the event of concurrent illness, AEs, or other reasons concerning the health or wellbeing of the subject, or in the case of lack of cooperation.

A subject (or a legal representative) has the right to withdraw from the study at any time and for any reason without prejudice to their future medical care by the investigator at the institution.

The investigator and/or sponsor can decide to withdraw a subject from investigational product and/or other protocol-required therapies, protocol procedures, or the study as a whole at any time prior to study completion for the following reasons:

- Subject no longer experiences clinical benefit as determined by the investigator. If study treatment is withdrawn for this reason, the date this decision is to be recorded and every

effort should be made to continue safety evaluations, tumour assessments, and collection of subsequent anticancer treatment information and follow-up information for survival.

- The investigator feels it is not in the best interest of the subject to continue on study.
- Subject participation in another clinical study using an investigational agent or investigational medical device.
- Necessity for treatment with other systemic anticancer therapy (non-protocol defined).
- Necessity for withholding study drug for greater than 6 weeks for study-treatment related AEs.
- Refusal of sexually active fertile subjects (excluding subjects who have been sterilised) to use medically accepted methods of contraception.
- Female subjects who become pregnant.
- Request by the sponsor.
- Subject request to discontinue study treatment (with or without concurrent withdrawal of informed consent).
- Significant noncompliance with the protocol schedule in the opinion of the investigator or the sponsor
- Unacceptable side effects the investigator feels may be due to study treatment.

In addition, if any of the following occur, no further treatment will be administered:

- Cumulative kidney absorbed dose exceeds 23 Gy.
- Cumulative BM absorbed dose exceeds 1.5 Gy during core trial or up to 2 Gy during additional cycles, as determined by dosimetry of peripheral blood samples and imaging.
- Subject has not sufficiently recovered from an adverse event despite extension of the dosing interval by 4 weeks (such as delayed grade 3-4 haematotoxicity)
- Hypersensitivity to the active substance or to any of the excipients of the study drugs
- Radiological disease progression

All cases of discontinuation will be discussed between the investigator and the sponsor.

A subject can also withdraw their consent to the treatment period but agree to take part in 24-month follow-up period.

If a subject is considered Not Evaluable for DLT due to withdrawal during DLT assessment period, he/she will be replaced by another subject.

In phase I, a cohort will be considered as completed once three subjects of the cohort complete Cycle 2 or discontinue early during Cycle 2. If subjects discontinue for any reason other than a DLT (e.g. disease progression) before end of Cycle 2, they might be replaced.

The phase I will be terminated once the MTCA has been determined. The phase II is designed with early stopping criteria, allowing any cohort to be closed early in case of futility.

A specific site or a given cohort can also be discontinued or the entire study may be terminated at any time if the sponsor judges it necessary for any reason. In that case, all scheduled procedures and assessments for subjects who are still in the study will be performed. Some possible reasons for the closure of a study site may include:

- failure of the investigator staff to comply with the protocol or with the Good Clinical Practice (GCP) guidelines.
- safety concerns.
- inadequate subject recruitment.

In case of premature discontinuation of a site or the complete study, depending on the reason(s) for the discontinuation, the sponsor will notify the investigator(s) affected in writing as to whether the ongoing subjects should continue the remaining IRPP dose administration(s).

Should, at the start of the study, 20 consecutive subjects fail screening due to Ga-OPS202 PET/CT negative for sstr2 with all the other inclusion/criteria met, the administration of Ga-OPS202 and subsequent PET imaging will be stopped. Selection of sstr2-positive tumours for the treatment with Lu-OPS201 will be revised in a protocol amendment.

### 1.3.3 *Schedule of assessments*

The phase I study design with and without additional cycles are shown in Figure 1 and Figure 2.

**Figure 1 Phase I Study Design Scheme (Without Additional Cycles)**

\* ceCT  
either  
each PI

**Figure 2 Phase I Study Design Scheme (With Additional Cycles)**

\* ceC  
or sep

Pharmacokinetics, biodistribution and dosimetry endpoints and measurement timepoints for phase II will be defined according to the phase I results.

The current protocol may be amended at the end of the phase I to define the phase II design.

### 1.3.4 *Planned sample size*

#### Sample Size Determination for Phase I

This is primarily a descriptive safety and tolerability study. The total number of subjects is not based on a formal statistical sample size calculation.

The actual sample size required to adequately determine the MTCA/MTSA during phase I depends on the initial activity, rate of radioactivity escalation and the observed radioactivity-toxicity and radioactivity/organ absorbed dose relationships. Simulation studies have been performed to quantify the operational characteristics (ie, precision of the MTCA/MTSA, sample size, number of subjects being over/under dosed) of the adaptive radioactivity-escalation design under a number of plausible escalation-DLT relationship scenarios. Based on experience, the chosen sample size of 3-5 subjects per cohort is considered to be sufficient to fulfil the objectives of the study. It is anticipated that between 15 and 30 subjects will be required to establish the MTCA or maximum administered cumulative activity (MACA).

#### Sample Size Determination for Phase II

The sample size is calculated using Simon's optimal two-stage design based on the ORR rate (complete response (CR) + partial response (PR)) following  $^{177}\text{Lu}$ -OPS201 treatment.

For the Simon's optimal two-stage design, the hypotheses that will be tested for each cohort are:  $H_0: \text{ORR} \leq \text{ORR}_0$  versus the alternative  $H_1: \text{ORR} > \text{ORR}_0$  where ORR is the true objective response rate following  $^{177}\text{Lu}$ -OPS201 treatment that warrants further clinical development, and  $\text{ORR}_0$  is the minimum objective response rate to be excluded from further clinical development. The thresholds for ORR and  $\text{ORR}_0$  may be updated based on results from phase I and the advances in scientific knowledge.

ORR will be analysed at the end of Stage 1 (6 weeks after the second  $^{177}\text{Lu}$ -OPS201 administration (Cycle 2) of the core treatment period of the last evaluable subject of the Stage 1 cohort for each type of cancer). If the observed number of responders is below a predefined threshold, the respective study cohort will be stopped for futility. Otherwise, additional subjects will be treated to complete the planned enrolment. At the end of Stage 2, the null hypothesis will be rejected depending on the total observed number of responders based on a predefined threshold.

For the SCLC cohort, with 69 response evaluable subjects, there will be 90% power to test a null hypothesis ORR rate of 23% and an alternative hypothesis ORR rate of 40% at one-sided significance level of  $\alpha=0.05$ . The first stage consists of 29 subjects. If seven responses or less are seen in the first 29 subjects then the trial is stopped. Otherwise accrual continues to a total of 69 response evaluable subjects. Approximately 76 subjects are planned to be enrolled to account for 10% study dropout.

For the BC cohort, with 87 response evaluable subjects, there will be 90% power to test a null hypothesis ORR rate of 12% and an alternative hypothesis ORR rate of 25% at one-sided significance level of  $\alpha=0.05$ . The first stage consists of 33 subjects. If four responses or less are seen in the first 33 subjects then the trial is stopped. Otherwise accrual continues to a total of 87 response evaluable subjects. Approximately 96 subjects are planned to account for 10% study dropout.

## 2 SUBJECT POPULATIONS (ANALYSIS SETS)

### 2.1 Eligibility screened population

All subjects screened (i.e. who signed the informed consent).

## 2.2 Efficacy

### 2.2.1 *Intention-To-Treat population (ITT)*

All subjects who received at least one dose of  $^{177}\text{Lu}$ -OPS201 in the phase II of the study.

### 2.2.2 *Per Protocol population (PP)*

All subjects in the ITT population in the phase II of the study who have measurable disease at baseline, have at least one post baseline response assessment and no major protocol deviations occurred that could affect efficacy analysis.

The PP population will be used for the analyses of ORR, DCR, PFS, OS, TTP, TTR and DoR.

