##### Phase II

- To evaluate the efficacy of  $^{177}\text{Lu}$ -OPS201 using Response Evaluation Criteria In Solid Tumours (RECIST) v1.1 and/or Positron Emission Tomography Response Criteria In Solid (PERCIST) v1.0 criteria, volumetric CT and modified PERCIST using  $^{68}\text{Ga}$ -OPS202 PET scans and modified RECIST using the  $^{68}\text{Ga}$ -OPS202 avid lesions.
- To evaluate PFS until long-term follow-up visits up to 2 years after the EOCT Visit.
- To estimate the 1-year overall survival (OS) rate.
- To further evaluate the safety profile of  $^{177}\text{Lu}$ -OPS201.
- To evaluate the association between uptake on  $^{68}\text{Ga}$ -OPS202 PET/CT with tumour response to  $^{177}\text{Lu}$ -OPS201 therapy.
- To determine the uptake of  $^{68}\text{Ga}$ -OPS202 in tumour lesions expressing sstr2 on PET/CT images and estimate its correlation with the uptake on  $^{177}\text{Lu}$ -OPS201 SPECT/CT.
- To evaluate the impact of  $^{177}\text{Lu}$ -OPS201 on the health-related quality of life of treated subjects.

SAP Final: Version 2.0: [03 January 2020]

12/57

- To estimate the proportion of sstr2-positive tumour lesions by  $^{68}\text{Ga}$ -OPS202 PET/CT scans as assessed by standardised uptake volume (SUV) in subjects screened for  $^{177}\text{Lu}$ -OPS201 treatment.
- To further assess some PK and dosimetry parameters of  $^{177}\text{Lu}$ -OPS201 based on the phase I results.

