**Table 2 Primary and Secondary Tumour Activity Endpoints and Evaluations**

Measure	Timepoint	Variable	Endpoint
Tumour size (longest diameter)	Screening [a] and 6 weeks after each $^{177}\text{Lu}$ -OPS201 administration (each cycle)	Tumour response according to RECIST v1.1	
 
ORR
 
BOR
 
PFS (complemented with events of death)
 
DRR (CR or PR lasting <math>\geq 6</math> months)
 
DCR
 
TTP
 
TTR
 
DoR
 

Tumour size (longest diameter)	Screening [a] and 6 weeks after second $^{177}\text{Lu}$ -OPS201 administration (second cycle)	Tumour response according to mGa-RECIST; Metabolic tumour response by $^{18}\text{F}$ -FDG-PET – PERCIST v1.0 and $^{68}\text{Ga}$ -OPS202 by mGa-PERCIST*	
 
ORR
 
BOR
 

Tumour volume	Screening [a] and 6 weeks after each $^{177}\text{Lu}$ -OPS201 administration (each cycle)	Mean change (%) in tumour volume assessed by volumetric CT/MRI	% change from baseline in tumour volume
Event of death	1 and 2 years	Death count	OS
$\text{SUV}_{\max}$ and $\text{SUV}_{\text{mean}}$	Screening [a] and 6 weeks after second $^{177}\text{Lu}$ -OPS201 administration (second cycle)	sstr2 targeted tumour uptake by $^{68}\text{Ga}$ -OPS202- PET/CT	Change in tumour uptake on $^{68}\text{Ga}$ -OPS202 PET/CT scan

Measure	Timepoint	Variable	Endpoint
SUL max and SUL mean	Screening [a] and 6 weeks after second  Lu-OPS201 administration (second cycle)	Tumour-to-background ratio by  F-FDG-PET using PERCIST v1.0	Quantitative changes in tumour-to-background  F-FDG-PET uptake
SUV max and SUV mean	Screening [a] and 6 weeks after second  Lu-OPS201 administration (second cycle)	 Ga-OPS202 uptake and  Lu-OPS201 therapy response	Change in  Ga-OPS202 uptake on PET scan in subjects screened for  Lu-OPS201 treatment as compared to clinical response and ORR

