**Table 6 Date of Progression or Censoring for DOR**

Situation	Date of progression or censoring	Outcome
Death or disease progression between planned disease assessments	Date of death or first disease assessment showing disease progression, whichever occurs first	Event
Surgical resection or subsequent anticancer treatment started before disease progression or death (without disease progression beforehand)	Date of last disease assessment prior to surgery or start of subsequent anticancer treatment	Censored
Death or disease progression after missing two or more consecutively scheduled disease assessments	Date of last disease assessment visit without documentation of disease progression before the first missed visit	Censored
Alive and without disease progression	Date of last disease assessment	Censored

- Mean change (%) in tumour volume at 6 weeks after each  $^{177}\text{Lu}$ -OPS201 administration (each cycle) compared to baseline, as assessed by volumetric CT/MRI.
- OS at 1-year and 2-year follow-up as determined from start of study treatment until occurrence of death of any cause. Subjects who were lost to follow-up or who were still alive at the time of analysis will be censored at the last day the subject was known to be alive or data cut-off date, whichever occurs first. OS will be calculated as follows:
  - OS (months) = (Death or Censoring Date – First Dose Date + 1)/30.4375
  - Quantitative changes (SUV normalised by lean body mass ( $\text{SUL}_{\text{max}}$  and  $\text{SUL}_{\text{mean}}$ ) in tumour-to-background  $^{18}\text{F}$ -FDG-PET uptake using PERCIST version 1.0, from Screening to 6 weeks after second  $^{177}\text{Lu}$ -OPS201 administration (second cycle).
  - Change in  $^{68}\text{Ga}$ -OPS202 uptake on PET scan after the second  $^{177}\text{Lu}$ -OPS201 administration (second cycle) as assessed by  $\text{SUV}_{\text{max}}$  and  $\text{SUV}_{\text{mean}}$  in subjects screened for  $^{177}\text{Lu}$ -OPS201 treatment as compared to clinical response and ORR.
  - Correlation between tumour uptake on  $^{68}\text{Ga}$ -OPS202 PET/CT (assessed based on  $\text{SUV}_{\text{max}}$  and  $\text{SUV}_{\text{mean}}$ ) at screening with tumour response to  $^{177}\text{Lu}$ -OPS201 therapy from Screening to 6 weeks after second  $^{177}\text{Lu}$ -OPS201 administration (second cycle).

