### **3.2 Analysis methods**

#### **3.2.1 Efficacy**

##### **3.2.1.1 Therapeutic Efficacy of Lu-OPS201**

Tumour response will be evaluated by the ICL. Phase I analyses on tumour responses will be using the MTCA evaluable population. Phase II analyses on tumour responses will be using the ITT population and the PP population.

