- OS is defined as the time from the date of first dose of  $^{177}\text{Lu}$ -OPS201 to the date of death due to any cause. Subjects who have not died will be censored at the date of last contact which may be identified from a visit date or any study assessment (physical examination, vital signs, ECOG performance status, ECG, study drug record, radiological evaluation, laboratory sampling, concomitant or follow-up procedures), AE, medication, or disposition information. OS will be calculated using the Kaplan-Meier method. One-year and two-year survival are defined as the subject survival probability at 1 year and 2 years, respectively, after the date of first dose of  $^{177}\text{Lu}$ -OPS201. One-year and two-year survival probability along with the associated 2-sided 95% confidence intervals, will be provided. If there are a sufficient number of OS events (i.e., deaths), median OS time, first and third quartiles and associated 95% 2-sided confidence intervals, will be estimated using the Brookmeyer-Crowley method ([Brookmeyer, 1982](#)). Kaplan-Meier OS curves also will be provided.
- DCR by RECIST v1.1, defined as the percentage of subjects who have achieved a response of CR, PR or stable disease, will be analysed and summarised in the same manner as ORR.
- TTP by RECIST v1.1, defined as the time from date of first dose of  $^{177}\text{Lu}$ -OPS201 to the date of first documentation disease progression as determined by the investigator, will be analysed and summarised in the same manner as PFS.
- TTR by RECIST v1.1, defined as the time from the date of first dose of  $^{177}\text{Lu}$ -OPS201 to the date of the first documentation of a response (CR or PR whichever occurs first) in a subject who responded, will be analysed and summarised in the same manner as PFS.
- DoR by RECIST v1.1, defined as the time from date of first documentation of response (CR or PR whichever occurs first) to the date of disease progression or to death due to any cause, whichever occurs first, will be analysed and summarised in the same manner as PFS.

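### Phase II OS and PFS are assigned to a per-protocol set that requires a post-baseline response assessment, and the SAP does not reconcile this with its efficacy methods or name a main set

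*SAP*

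**What the plan says.** Section 2.2.2 admits to PP those ITT subjects who have measurable disease at baseline, "have at least one post baseline response assessment and no major protocol deviations occurred that could affect efficacy analysis". It then fixes the use of the set: "The PP population will be used for the analyses of ORR, DCR, PFS, OS, TTP, TTR and DoR". ITT (section 2.2.1) is every phase II subject given at least one dose of the therapy.

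The survival objective in section 1.1.2 is "To estimate the 1-year overall survival (OS) rate". Section 3.1.2 gives the endpoint as "OS at 1-year and 2-year follow-up as determined from start of study treatment until occurrence of death of any cause", and section 3.2.1.1 agrees: "OS is defined as the time from the date of first dose of" the therapy, ending at death from any cause. Neither definition needs a scan.

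Three other places mention the sets:

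- Section 3.2.1.1 opens with "Phase II analyses on tumour responses will be using the ITT population and the PP population".
- Section 2.7 makes PP primary for the primary efficacy endpoint and leaves an ITT analysis optional.
- Section 3.2.8 compares ITT with PP for the primary efficacy and dosimetry analyses.

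None of the three names OS.

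**The concern.** Scans are due 6 weeks after each administration, or at first clinical signs of progression. A subject who is treated once and dies before any scan belongs to ITT but not to PP. On PP that death is not counted. Entry to the set then depends on something that happens after the OS clock has started, and the subjects lost this way are all early deaths. The 1-year OS rate is a named phase II objective in a single-arm setting, where there is no control arm in which the same selection would occur.

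PFS raises a different question. Table 4 counts a death before the first planned assessment as an event, a rule written for a set that keeps such subjects. Section 2.2.2 nevertheless names PP for PFS.

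**Working it through.** **1. Which set does the SAP give to OS?** Section 2.2.2 names PP. Section 3.2.1.1 names ITT and PP, but for tumour responses. Table 2 puts OS in its own row, with the measure "Event of death", apart from the RECIST v1.1 row that holds ORR and PFS. The same table's title, however, calls all its rows tumour activity endpoints. No sentence assigns OS to ITT by name, and none says which set is main for OS or PFS.

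**2. The plan's own figures.** The SAP states no OS rate, no OS precision and no share of early deaths. Its nearest figure is the non-evaluable allowance in section 1.3.4:

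- SCLC: 69 × 1.1 = 75.9, planned as 76, so 7/76 = 9.2% not evaluable.
- BC: 87 × 1.1 = 95.7, planned as 96, so 9/96 = 9.4% not evaluable.

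The early-termination probabilities in section 3.2.16 also reproduce by exact binomial: P(X ≤ 7 | n = 29, p = 0.23) = 0.6555 and P(X ≤ 4 | n = 33, p = 0.12) = 0.6374. They depend only on response-evaluable counts, so the set used for OS does not touch them.

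**3. Effect on the 1-year OS rate.** Let S be the rate in all treated subjects and e the share who die without a scan. Assume that everyone alive at 1 year is in PP and that PP makes no other exclusions. Then

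OS on PP = S / (1 − e).

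The denominator is below 1 whenever e > 0, so this mechanism never lowers the estimate. Both S and e are assumptions. The lower e of 2% allows for scans done early at clinical progression. The upper e takes every planned non-evaluable subject to have died unscanned.

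| Assumed S | e = 2% | e = 5% | e = 7/76 | e = 9/96 |
|---|---|---|---|---|
| 20% | 20.4% | 21.1% | 22.0% | 22.1% |
| 30% | 30.6% | 31.6% | 33.0% | 33.1% |
| 60% | 61.2% | 63.2% | 66.1% | 66.2% |

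**4. Scale.** The 95% half-width at 30% is 1.96 × √(0.3 × 0.7 / n), which is 10.3 points for n = 76 and 9.2 points for n = 96. At S = 30% the shift is 0.6 to about 3 points. It is smaller than sampling error, but it has a fixed direction and does not shrink with more subjects.

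**5. PFS.** On ITT, the Table 4 rule for death before the first planned assessment has its full effect. On PP it can reach only a subject who was scanned early, at clinical signs, and then died before the planned scan. The row for subjects with no evaluable post-baseline assessment is likewise nearly empty on PP. The censoring table thus presupposes an all-treated set, while section 2.2.2 names another.

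**The case against.** The strongest reply is that section 3.2.1.1 already plans OS on both sets. Its opening is the only population statement in the section on therapeutic efficacy, and the OS bullets stand under it. If it excluded OS because OS is not a tumour response, phase I OS would have no analysis set, since the same opening is what gives phase I efficacy its set. Section 2.2.2 also says that PP will be used, not that it alone will be. This reading is reasonable, and it stops one from saying that OS will certainly be reported without the early deaths. It does not settle the matter: section 2.2.2 names OS and PP explicitly, section 3.2.1.1 does not name OS, and neither ranks the sets.

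Three further points stand:

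- Early unscanned deaths would not be hidden. Section 3.2.5 tabulates the populations with reasons for exclusion, and section 3.2.2.1 lists deaths.
- PP exclusions for protocol deviations or lack of measurable disease could move OS in either direction.
- Section 5 cuts the study report to listings after premature closure, and no OS or PFS output remains.

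A reader might also infer that PFS is shown to be biased, or that the ITT analysis of ORR is in doubt. The documents support neither. PFS sits in the RECIST row of Table 2, so section 3.2.1.1 can be read as planning it on both sets. For ORR, sections 3.2.1.1 and 3.2.8 already plan ITT, so the optional wording in section 2.7 is an editorial mismatch.

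**Conclusion.** The point holds as a minor one, with moderate confidence. A stated rule places OS on a set conditioned on a post-treatment scan. If it is followed, deaths before any scan are removed and the 1-year rate is pushed upward through that route. Whether it would be followed alone is unclear, because sections 2.2.2 and 3.2.1.1 are not reconciled. For PFS the finding is only that the main set is unnamed and that Table 4 fits an all-treated set better.

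The figure of 30.6% to 33.0% (33.1% with the BC allowance) for an assumed 30% illustrates the size and is not an estimate from the SAP. A constant death rate with every death before week 6 unscanned would give a larger shift, to about 34% from 30%. The documents do not support leaning on that: it ignores scans at clinical progression and implies about 13% lost, more than the whole non-evaluable allowance. The issue has practical effect only if the phase II analyses are run or the plan is reused.

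**What to change.** In section 2.2.2, remove OS and PFS from the sentence that lists the PP analyses. In section 2.7, name ITT as defined in section 2.2.1 as the main set for OS and PFS, with PP as a sensitivity analysis. Leave the Simon test on response-evaluable subjects as it is. As an editorial matter, align the optional ITT wording for ORR in section 2.7 with sections 3.2.1.1 and 3.2.8.

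The cost is a few sentences of SAP text. The ITT set already exists, no new data are needed, and the Simon counts, stopping thresholds and power do not change.
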